## I. Purpose

Cannabidiol (CBD) is a chemical constituent found in cannabis that does not have intoxicating effects; it is thought to curtail the psychoactive effects of delta-9-tetrahydrocannabinol (THC), the primary psychoactive component of cannabis (see Mechoulam et al., 2002; Fusar-Poli et al., 2009). While studies have established the analgesic effects of THC and similar cannabinoid type-1 (CB1) receptor agonists across species (e.g., Cooper et al., 2013; Craft et al., 2013; Maguire et al., 2013), the psychoactive effects and abuse potential of these drugs decrease enthusiasm for their potential clinical utility.

Preclinical studies have demonstrated that CBD alone is effective in producing analgesia in models of neuropathic pain (Costa et al., 2007; Toth et al., 2010; Ward et al., 2011 & 2014) and non-neuropathic pain (Maione et al., 2010). Importantly, CBD does not elicit the behavioral effects indicative of abuse potential (Ward et al., 2014). Recent clinical studies have suggested that the 1:1 combination of THC:CBD in an oromucosal spray administered as an adjuvant therapy with concomitant analgesics produces analgesia in patient populations with intractable pain (i.e., Langford et al., 2013; Portenoy et al., 2012). However, to date, there have been no controlled studies investigating the analgesic effects of CBD alone. Thus, CBD's analgesic effects in humans cannot be distinguished from those of THC. Establishing the analgesic effects of CBD alone will fill a critical gap in our knowledge about the potential therapeutic effects of this drug.

## II. Introductory Statement

Recent clinical studies have suggested that the combination of THC and cannabidiol (CBD), the primary chemicals in cannabis, produces pain-relieving effects in patient populations (i.e., Langford et al., 2013; Portenoy et al., 2012). However, to date, there have been no controlled studies investigating the pain-relieving effects of CBD administered alone. For this study, the pain-relieving effects of CBD will be assessed in healthy, non-substance-using adults between 21-50 years old over 4 outpatient laboratory sessions. The physiological and subjective effects of CBD will also be measured. This study, designed to establish the analgesic effects of CBD alone, will fill a critical gap in our knowledge about the potential therapeutic effects of this drug.

### III. General Investigational Plan

This within-subject, double-blind, placebo-controlled study will assess the analgesic effects of a range of cannabidiol (CBD) doses (0, 200, 400, or 800 mg, po). Normal, healthy volunteers with no current pain or substance use will participate in 4 outpatient laboratory sessions over the course of 4 weeks during which the analgesic effects of CBD will be assessed using the Cold-Pressor Test (CPT), a laboratory model of pain which has predictive validity for the clinical use of analgesics. The order of CBD dose will be counter-balanced across participants; **Table 1** illustrates a representative dosing schedule. Secondary measures will include subjective and physiologic effects of CBD, and the CPT, subjective mood and drug effects, and vital signs will be measured before and at specified time points after CBD administration. Determining the efficacy of CBD in an experimental model of pain will provide important endpoints (i.e., dose, time course) of this effect to further investigate the potential role for clinical use of CBD as an analgesic.

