**Table 1. Representative Dosing Schedule**

Day	M	T	W	Th	F
Week 1	Subject 1	Subject 2	Subject 3	Subject 4	Subject 5
Session	1	1	1	1	1
CBD (mg)	0	200	400	800	0
Week 2	S1	S2	S3	S4	S5
Session	2	2	2	2	2
CBD (mg)	200	400	800	0	200
Week 3	S1	S2	S3	S4	S5
Session	3	3	3	3	3
CBD (mg)	400	800	0	200	400
Week 4	S1	S2	S3	S4	S5
Session	4	4	4	4	4
CBD (mg)	800	0	200	400	800

The primary outcome measures for this study will be the dose-dependent analgesic and subjective effects of CBD. There will be 4 dose conditions under which these endpoints will be measured (0, 200, 400, and 800 mg CBD). A priori planned comparisons will be performed to determine dose-dependent effects of CBD relative to placebo. We hypothesize that CBD will elicit dose-dependent increases in analgesia. We also hypothesize that CBD will fail to produce subjective effects of intoxication ('Solution liking,' 'Good solution effect,' etc.).

IV. Protocol

*PARTICIPANTS:*

All research volunteers (N=18) will be between 21 and 50 years old, male or non-pregnant female, and healthy (according to medical and psychiatric examinations). It is expected that 50% of applicants will be female and that 40-50% of applicants will be non-Hispanic Caucasian, 25-30% will be Hispanic, 15-20% will be non-Hispanic Black or African American, 5-10% will be Asian or Pacific Islanders, and less than 1% will be Native Americas, Eskimos, or Aleuts. We will not accept volunteers who are substance-users, on parole or probation, nor those previously convicted of a crime of violence. The extensive medical screening assures that only healthy volunteers will be used. Any subject with abnormal medical findings will be offered referral for treatment. Likewise, if an individual is dependent on any drugs, with the exception of nicotine or caffeine, he/she will be offered referral to an appropriate treatment program.

*STUDY INCLUSION AND EXCLUSION CRITERIA* (list in outline form):

INCLUSION CRITERION	METHOD OF ASCERTAINMENT
1. Adults between the ages of 21 and 50	Clinical interview and verification with identification
2. Able to perform study procedures	Practice sessions
3. Women practicing an effective form of birth control (condoms, diaphragm, birth control pill, IUD)*	Self-report during interview
EXCLUSION CRITERION	METHOD OF ASCERTAINMENT
1. Female subjects who are currently pregnant or breastfeeding	Clinical interview, physical examination, serum HCG

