**STATSTICAL ANALYSIS PLAN**

Repeated measures analysis of variance (ANOVA) with planned comparisons were used to assess cannabidiol’s dose-related effects on measures of pain and subjective drug effects associated with abuse liability. For each participant under each dose condition, pain threshold and tolerance were calculated as the difference from baseline CPT (pre-drug administration) values. Subjective pain ratings (Pain Intensity and Bothersomeness Scales) were also measured as a function of change from the baseline response. Changes scores from each of the three active cannabidiol dose strengths were compared to placebo (i. e., 0 mg vs 200 mg; 0 mg vs 400 mg; 0 mg vs 800 mg) for each of the measures specified above. Results were considered statistically significant when *p* values were equal to or less than 0.01 using Huynh-Feldt corrections (SuperANOVA, Abacus Concepts, Inc., Berkley, CA).

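### Four doses cannot be spread evenly over four sessions with 18 participants, and the ANOVA has no session term, so session drift slightly offsets the dose contrasts and, more importantly, inflates their error

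*Combined protocol and SAP*

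**What the plan says.** Section III of the protocol describes a within-subject study of four doses over four weekly sessions and states: "The order of CBD dose will be counter-balanced across participants". The schedule that illustrates this is headed "Table 1. Representative Dosing Schedule". It shows four cyclic orders, with Subject 5 repeating the order of Subject 1. The Participants paragraph of section IV sets the sample size at 18. No number of participants per order is given, and there is no rule for replacing those who leave.

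The Statistical Analysis Plan states: "Repeated measures analysis of variance (ANOVA) with planned comparisons were used to assess" dose-related effects on pain and on subjective drug effects. The planned comparisons are "0 mg vs 200 mg; 0 mg vs 400 mg; 0 mg vs 800 mg", and results count as significant when p "values were equal to or less than 0.01 using Huynh-Feldt corrections". Pain threshold, tolerance and pain ratings are analysed as change from the same session's pre-drug cold pressor test (CPT). No session, period or sequence factor is named.

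**The concern.** Counterbalancing is meant to stop changes over visits (habituation, practice, expectation) from being read as dose effects. It does so exactly only if every dose occurs equally often in every session. When it does not, part of the drift over visits enters the dose contrasts.

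Even under perfect balance, drift that is not modelled stays in the residual and widens the error against which dose is tested. With 18 participants and a 0.01 threshold there is little precision to spare. The direction also matters. One hypothesis in section III is that CBD will not produce subjective effects of intoxication, and a test with an inflated error term makes that null result easier to obtain.

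**Working it through.** **Inputs.** From the documents: N = 18; 4 doses; 4 sessions; the four cyclic orders of Table 1; threshold 0.01. Assumed: two-sided tests; one score per participant per dose (72 values) with a pooled error term; linear drift of b residual SD per session. The documents give no drift size and no basis for N = 18, so there is no sample-size figure of the plan's own to reproduce.

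**1. Balance.** Each dose would have to appear 18/4 = 4.5 times in each session. No set of orders achieves this. The nearest split over the four Table 1 orders is 5/5/4/4.

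**2. Offset in the contrasts.** For each dose, mean session position = sum of (participants on the order × session in which that order gives the dose) / 18. If the Table 1 rotation continues to Subject 18, the first two orders get 5 participants each:

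- 0 mg: (5×1 + 5×4 + 4×3 + 4×2)/18 = 45/18 = 2.50
- 200 mg: (5×2 + 5×1 + 4×4 + 4×3)/18 = 43/18 = 2.39
- 400 mg: (5×3 + 5×2 + 4×1 + 4×4)/18 = 45/18 = 2.50
- 800 mg: (5×4 + 5×3 + 4×2 + 4×1)/18 = 47/18 = 2.61

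The offsets from placebo are -0.11, 0 and +0.11 sessions. The six possible 5/5/4/4 splits give 18 contrasts: 4 have offset 0, 12 have 0.11 and 2 have 0.22 in absolute value. Bias under linear drift is the offset times b, so at most 0.22b. If two participants are lost and completers are analysed, the largest offset lies between 0 and 0.50 sessions, depending on the starting split and on who leaves.

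**3. Error term without session.** Every participant attends sessions 1-4, so the drift sum of squares is 18 × 5 × b² = 90b², where 5 is the sum of squared deviations of 1-4 from 2.5. Under the rotation split, dose absorbs 18 × 2 × (1/9)² × b² = 0.44b². Error df are 72 - 18 - 3 = 51. The residual variance is therefore multiplied by 1 + 89.56b²/51 = 1 + 1.756b². Power is for the 800 mg contrast at an assumed true effect of 1.0 SD.

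| b (SD per session) | Residual variance | SE | Actual type I error, 800 mg | Power without session | Power with session |
|---|---|---|---|---|---|
| 0.10 | +1.8% | +0.9% | 0.009 | 63% | 62% |
| 0.25 | +11% | +5% | 0.007 | 61% | 62% |
| 0.50 | +44% | +20% | 0.003 | 49% | 62% |

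**4. With session in the model.** Error df fall from 51 to 72 - 18 - 3 - 3 = 48. Contrast variance rises from 2/18 = 0.1111 to at most 0.1118 of the residual variance, and 0.1118/0.1111 = 1.006. Bias from additive drift is zero.

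**The case against.** Four points on the other side have weight.

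- *Table 1 is only representative.* This is correct, and it limits what can be said about offsets. For example, 16 participants on the square plus one each on 0-200-400-800 and 800-400-200-0 give every dose a mean position of (40 + 5)/18 = 2.5, so linear drift would cause no bias. Cell counts would still be unequal, and drift would still sit in the error term.
- *The same-session baseline already removes drift.* For CPT threshold, tolerance and pain ratings, a shift common to the pre- and post-dose tests cancels, and only drift in the change score remains. The practice session before admission may reduce it further. This stands for the pain outcomes. It does not help the Solution Rating Form, which first appears 30 minutes after dosing in Table 2 and so has no pre-dose value to subtract.
- *The drift is assumed.* This also stands. At 0.10 SD per session leaving session out costs nothing, and at 0.25 SD it costs about one point of power. A material loss needs drift near 0.5 SD.
- *The error is in the safe direction.* Type I error falls below 0.01. That is reassuring for a claim of analgesia, but not for a hypothesis that is supported by a non-significant result.

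A reader might also infer that weekday is confounded with dose, because Table 1 lays out participants by day. It is not: each participant keeps one weekday for all four sessions, so weekday cancels within person.

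**Conclusion.** The point holds at moderate size. Exact counterbalancing is impossible at N = 18, and the analysis has no term to compensate. Bias in the contrasts is small: between none and about a fifth of one session's drift under a 5/5/4/4 split of the Table 1 orders, and possibly more after unequal dropout. The main consequence is lost precision, which ranges from negligible at 0.1 SD of drift per session to a 20% larger standard error at 0.5 SD. These figures rest on linear drift of assumed size and on a pooled error term. The point weighs most on Solution Rating Form items, where drift enters in full and a conservative test favours the hypothesis of no intoxication effects.

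Two stronger readings are not supported. One is that the dose contrasts are seriously biased by order; the offsets are too small for that. The other is that omitting session raises the false-positive rate; in the cases calculated it lowers it.

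**What to change.** Add session (1-4) as a fixed factor in every dose analysis, for pain and for subjective outcomes. This removes bias from additive drift and takes the drift out of the error. It costs 3 error df (51 to 48) and under 1% in contrast variance, and needs no extra participants. It remains feasible if dosing is complete, as the past tense of the Statistical Analysis Plan suggests.

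Report the number of participants on each dose order, as assigned and as analysed, so that the achieved balance can be seen.

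A session term does not deal with first-order carryover. In the cyclic orders of Table 1 each dose always follows the same dose (placebo follows 800 mg whenever it is not first), and neither the session term nor equal numbers per order changes that.

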**Table 1. Representative Dosing Schedule**

Day	M	T	W	Th	F
Week 1	Subject 1	Subject 2	Subject 3	Subject 4	Subject 5
Session	1	1	1	1	1
CBD (mg)	0	200	400	800	0
Week 2	S1	S2	S3	S4	S5
Session	2	2	2	2	2
CBD (mg)	200	400	800	0	200
Week 3	S1	S2	S3	S4	S5
Session	3	3	3	3	3
CBD (mg)	400	800	0	200	400
Week 4	S1	S2	S3	S4	S5
Session	4	4	4	4	4
CBD (mg)	800	0	200	400	800

The primary outcome measures for this study will be the dose-dependent analgesic and subjective effects of CBD. There will be 4 dose conditions under which these endpoints will be measured (0, 200, 400, and 800 mg CBD). A priori planned comparisons will be performed to determine dose-dependent effects of CBD relative to placebo. We hypothesize that CBD will elicit dose-dependent increases in analgesia. We also hypothesize that CBD will fail to produce subjective effects of intoxication ('Solution liking,' 'Good solution effect,' etc.).

IV. Protocol

*PARTICIPANTS:*

All research volunteers (N=18) will be between 21 and 50 years old, male or non-pregnant female, and healthy (according to medical and psychiatric examinations). It is expected that 50% of applicants will be female and that 40-50% of applicants will be non-Hispanic Caucasian, 25-30% will be Hispanic, 15-20% will be non-Hispanic Black or African American, 5-10% will be Asian or Pacific Islanders, and less than 1% will be Native Americas, Eskimos, or Aleuts. We will not accept volunteers who are substance-users, on parole or probation, nor those previously convicted of a crime of violence. The extensive medical screening assures that only healthy volunteers will be used. Any subject with abnormal medical findings will be offered referral for treatment. Likewise, if an individual is dependent on any drugs, with the exception of nicotine or caffeine, he/she will be offered referral to an appropriate treatment program.

*STUDY INCLUSION AND EXCLUSION CRITERIA* (list in outline form):

INCLUSION CRITERION	METHOD OF ASCERTAINMENT
1. Adults between the ages of 21 and 50	Clinical interview and verification with identification
2. Able to perform study procedures	Practice sessions
3. Women practicing an effective form of birth control (condoms, diaphragm, birth control pill, IUD)*	Self-report during interview
EXCLUSION CRITERION	METHOD OF ASCERTAINMENT
1. Female subjects who are currently pregnant or breastfeeding	Clinical interview, physical examination, serum HCG
2. Current illicit drug use	Urine drug toxicology, clinical interview
3. Presence of significant medical illness (e.g., diabetes, cardiovascular disease, hypertension, hepatitis, clinically significant laboratory abnormalities, abnormal LFTs, blood pressure > 140/90)	Medical history, physical examination, laboratory tests, 12-lead ECG
4. Current parole or probation	Self-report during interview
5. History of heart disease	Clinical interview, abnormal ECG
6. Recent history of significant violent behavior	Self-report during interview

7. Major current Axis I psychopathology (e.g., major depressive disorder, bipolar disorder, suicide risk, schizophrenia)	Psychiatric interview
8. Current use of any prescription or over-the-counter medication	Medical history
9. Current chronic pain	Self-report during interview

\* For females of child-bearing age: The serum pregnancy test is performed during the screening procedure, and urine pregnancy tests are repeated on each visit. Since this test cannot detect the very early stage of pregnancy (10 day period between fertilization and implantation), an effective birth control method or sexual abstinence is required throughout study participation.

*SCREENING PROCEDURES:*

1) Initial telephone interviews will be carried out by research assistants and volunteers who have been trained by [name], during which time potential participants will be asked about their current and past drug use and general health. Individuals who are interviewed by telephone will be considered eligible for screening at the Substance Use Research Center if they are between ages 21-50, are not regular users of drugs, and self-disclose as medically and psychiatrically healthy, without chronic pain.

2) After initial determinations of eligibility, volunteers will come into the laboratory for their first screening visit. They will be asked to sign our study-specific screening consent form, allowing us to collect questionnaire data, conduct interviews, and obtain medical information. We will do an ECG test. Participants will be told that they will be taking part in a study investigating the effects of cannabidiol, an experimental oral medication taken by mouth in solution form.

3) Psychologists (e.g., the primary investigator and co-investigators) will conduct interviews and will provide a detailed explanation of the procedures outlined in the study consent form. The psychologist will also sign the screening consent form.

4) Laboratory tests will be performed that include urinalysis, urine drug toxicology, 12-lead electrocardiogram, and blood tests (complete blood count with differential, chemistry profile). A serum pregnancy test will be performed on all women during screening. All medical information will be evaluated by the study physicians.

5) Medical and psychiatric interviews will be conducted by a study physician in the Division on Substance Abuse and will include a physical examination and review of all medical results and study inclusion/exclusion criteria. All of the psychiatrists have completed at least 4 years of psychiatric training and most are Board Certified (those not Board Certified are in the process of obtaining certification). Based on the results of clinical interviews, physicians will confirm

whether volunteers have major current Axis I psychopathology (e.g., major depressive disorder, bipolar disorder, suicide risk, schizophrenia) requiring medical intervention.

6) During or after the physical examination, the study physician will discuss this study protocol with the volunteers and document their consent to the research study. The physician will then sign the study consent form. Study procedures will begin after the study physician verifies that participant meets inclusion/exclusion criteria, understands the medical risks of participation, and is capable of providing informed consent. The senior study physician will settle any disagreements among the study team as to a volunteer’s eligibility, and will make the final decision as to study participation. All procedures are consistent with the Division of Substance Abuse Guidelines for Investigators (9/8/08).

7) Because there is a proportion of the population that is unable or unwilling to tolerate pain induced by the Cold-Pressor Test, all potential participants will undergo a practice session prior to admission into the study. Participants also will practice completing the computerized questionnaires and performance tasks under supervision of laboratory staff to allow them to become familiar with these aspects of the protocol. This training day reduces variability in the data and provides both participants and researchers with important information about how an individual will respond to the test conditions.

*MEDICATION:*

**Cannabidiol (CBD):** Placebo or active CBD (0, 200, 400, or 800 mg), provided by Insys Therapeutics, Inc., will be administered orally in liquid solution form. For study session administration, both the active and placebo drug solutions will be masked in taste and smell by peppermint oil (Insys manufactures the matching placebo, which is then re-packaged by the NYSPI pharmacy and masked by a drop of peppermint oil).

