### **Laboratory Sessions and Cold Pressor Test (CPT):**

In the current study, there will be four laboratory sessions to assess the effects of a range of cannabidiol doses on analgesia. During the CPT test sessions, which will start and end at approximately 0900 and 1630hr, the analgesic, subjective, and physiological effects of cannabidiol will be determined repeatedly following a pretreatment of cannabidiol or placebo (see **Table 3**). Administration of cannabidiol will occur at 1000 hr. Baseline assessments will include measurements of analgesia (CPT), mood, blood pressure and heart rate. A breathalyzer test will be done before each session and urine samples will be tested for illicit drug use and, for women, pregnancy (prior to all sessions). Participants testing positive for drugs will be excluded from further participation. A light breakfast will be provided before CBD administration (e.g., bagel, juice, coffee).

The CPT, a well-established model for producing pain in humans (e.g., Chen et al., 1989; Conley et al., 1997; Zacny et al., 1996), will be performed once before and six times after drug administration and will last approximately 15 minutes. Our laboratory and others have shown that multiple CPTs can be carried out within the same day with little or no carryover effects between tests (e.g., Conley et al., 1997; Zacny et al., 1996), and it can be used to detect the analgesic effects of cannabinoids (Cooper et al., 2013). In this assay, the two dependent measures are latency to feel pain and latency to withdraw the hand from the cold water. Because previous research has shown that experimenters of the opposite sex influence responding to painful stimuli (Clark and Goodman, 1974; Clark and Mehl, 1971; Levine and De Simone, 1991), the sex of the experimenter will always be of the same sex as the research participant.

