The cold pressor apparatus will consist of two coolers filled with either warm (37°C) or cold (4°C) water with an aquarium pump that will circulate the water. The CPT will be performed seven times throughout the session. At the beginning of each CPT trial, the experimenter will read a standardized script describing the procedures to the participant. The participant will begin the test by placing the left hand into the warm water for three minutes. During the warm water immersion, the State Anxiety Inventory will be completed; blood pressure and heart rate will be measured. The participant will be instructed to remove his or her hand from the water after three minutes and skin temperature of the thumb pad will be measured. Another scripted statement will be read describing the CPT procedure to the participant, before the participant immerses his or her hand in the cold water. Participants will be instructed to report the first painful sensation, and to remove the hand when the stimulus can no longer be tolerated. Immediately after removing the hand from the cold water, blood pressure, heart rate, and skin temperature will then be measured. Upon withdrawal of the hand, participants will be asked to rate the pain and bothersomeness of the cold-water stimulus on a scale from 0 to 10, 0 being "not painful/bothersome at all" and 10 being "most painful/ bothersome feeling imaginable." They will additionally complete a shortened Cold Pressor Test-Visual Analog Scale (CPT-VAS) and report the sensory and affective dimensions of the pain experience with the Short Form-McGill Pain Questionnaire (SF-MPQ). The CPT-VAS

questionnaire will consist of 11 items presented one at a time. Participants will be instructed to mark on a 100 mm line labeled “not at all” on one end and “extremely” at the other end indicating how they feel at that moment. The following questions will be included in the CPT-VAS: “I feel...” “Like I am coasting,” “Confused,” “Dizzy,” “Drunk,” “Elated,” “Like I am floating,” “Light-Headed,” “Nauseated,” “Sedated,” “Sleepy,” “Stimulated.” Participants will again complete the State Anxiety Inventory. Pain dissipates rapidly after removal of the extremity from the cold water. Except for the acute stress associated with the pain test, there have been no known long-term consequences of this procedure.

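### A rise in analgesia with dose is hypothesised, but no planned comparison sets one active dose against another, no pain measure is ranked primary, and subjective effects are called both primary and secondary

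*Combined protocol and SAP*

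**What the plan says.** **Hypothesis and planned comparisons.** The text after the first Table 1, in the General Investigational Plan, says: "We hypothesize that CBD will elicit dose-dependent increases in analgesia". It adds: "A priori planned comparisons will be performed to determine dose-dependent effects of CBD relative to placebo". The SAP specifies a repeated measures ANOVA and names three comparisons, 0 mg against 200, 400 and 800 mg: "Changes scores from each of the three active cannabidiol dose strengths were compared to placebo". The significance level is 0.01 with Huynh-Feldt correction. Neither section describes a trend contrast, an ordered-dose model or a comparison between active doses.

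**Pain measures.** The section on Laboratory Sessions and the Cold Pressor Test (CPT) says that "the two dependent measures are latency to feel pain and latency to withdraw the hand from the cold water". The SAP analyses change from baseline in threshold and tolerance, and then adds: "Subjective pain ratings (Pain Intensity and Bothersomeness Scales) were also measured as a function of change from the baseline response". The same dose comparisons apply to all four. On the ratings, the CPT section says: "Upon withdrawal of the hand, participants will be asked to rate the pain and bothersomeness of the cold-water stimulus". Table 3 ends the cold immersion at withdrawal or at 180 s.

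**Status of subjective effects.** The opening paragraph of the General Investigational Plan says: "Secondary measures will include subjective and physiologic effects of CBD". The paragraph after Table 1 says: "The primary outcome measures for this study will be the dose-dependent analgesic and subjective effects of CBD".

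**The concern.** The hypothesis concerns how analgesia changes across doses, and the General Investigational Plan says the study should inform dose for later work. Differences from placebo answer a related but different question: which doses do something. A report could show all three doses better than placebo without any planned evidence on whether more drug gives more analgesia.

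The plan also gives no rule for pain measures that disagree. Disagreement is plausible, because the ratings follow an immersion whose length the participant sets. A drug that lengthens tolerance could leave the ratings unchanged or higher.

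Finally, a reader cannot tell whether the subjective-effects results belong to the primary claim, although the plan attaches a hypothesis to them.

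**Working it through.** **Inputs from the documents.** N = 18, within-subject, four doses (Participants; General Investigational Plan). Three placebo comparisons, four pain measures and a level of 0.01 (SAP). One baseline and six post-dose CPTs per session (CPT section). The plan gives no effect size, SD or power, so there is no stated figure to reproduce.

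**Assumptions.** Two-sided tests, one summary value per session, spherical errors, and effects in within-subject SD units. The SAP does not say how the six post-dose CPTs are combined, so the figures illustrate and do not describe the analysis as written.

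**Step 1: do the planned tests use dose order?** The standard error of a difference between two doses is √(2/18) = 1/3 SD, so each standardised difference is 3 × the difference in means. Take means 0/0.2/0.5/1.0 and exchange those for 200 and 800 mg, giving 0/1.0/0.5/0.2. Both sets give the placebo contrasts 0.6, 1.5 and 3.0. The omnibus numerator is 18 × Σ(mean − 0.425)²/3 = 18 × 0.5675/3 = 3.405 for both. The 800 minus 200 mg statistic moves from 3 × 0.8 = +2.4 to −2.4. As a set, the planned statistics are blind to order; only the dose labels on the three results carry it.

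**Step 2: what do the three results show?** Error df = 17 × 3 = 51, critical t = 2.676.
- Steep profiles: 200 mg significant and 800 mg not occurs in 79% of trials under a reversed profile (0/1.3/0.867/0.433) and 0.1% under a steep rise (0/0.433/0.867/1.3). The planned comparisons separate these well.
- Shallow profiles: all three are significant in 62% of trials for both 0/1.1/1.2/1.3 and 0/1.3/1.2/1.1. That outcome cannot tell them apart.

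**Step 3: the active-dose comparison.** Noncentrality = 3 × (800 mg effect − 200 mg effect).
- Steep rise: 3 × 0.867 = 2.60.
- Flat: 0.
- Mild fall: 3 × (−0.2) = −0.6.
- Shallow rise: 3 × 0.2 = 0.6.

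**Step 4: an ordered contrast for comparison.** Scores by mg, centred and divided by 50, are −7, −3, 1, 9, with sum of squares 140. For a flat 1 SD effect the contrast is −3 + 1 + 9 = 7, so noncentrality = 7/√(140/18) = 2.51. For the steep rise it is 11.27/2.789 = 4.04.

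Percentage of trials meeting each criterion, in the rising direction:

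| Profile (SD) | 800 mg significant, 200 mg not | mg contrast significant | mg contrast significant and active estimates rising | 800 vs 200 mg significant |
|---|---|---|---|---|
| Steep rise 0/0.433/0.867/1.3 | 79 | 91 | 76 | 48 |
| Flat 0/1/1/1 | 15 | 44 | 13 | 0.5 |
| Flat 0/1.3/1.3/1.3 | 7 | 72 | 16 | 0.5 |
| Mild fall 0/1.3/1.2/1.1 | 4 | 47 | 7 | 0.1 |
| Shallow rise 0/1.1/1.2/1.3 | 20 | 77 | 29 | 2 |

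Only the last column keeps flat and falling profiles near zero. Its price is low power: a 99% interval for the difference has half-width 2.676/3 = 0.89 SD.

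**Step 5: multiplicity.** Four measures × three comparisons = 12 tests. The simulated chance of any false positive is 10% for uncorrelated measures and 8% at correlation 0.7. For one measure with three comparisons sharing a placebo arm it is about 2.7%.

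**Step 6: subjective effects.** No arithmetic applies. Two paragraphs of the same section give them different status, and both are current text.

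**The case against.** The plan says its comparisons determine dose-dependent effects relative to placebo, and the SAP runs exactly those. That is a legitimate way to describe dose effects, and it distinguishes steep profiles. A reader might infer that no formal result bears on the hypothesis. The documents do not support that: the three comparisons bear on it, but do not test the rise itself.

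A reader might also infer that judging dose-dependence from which doses reach 0.01 is unreliable, since 800 mg significant and 200 mg not appears in 15% of flat 1 SD trials. That is one-sided. A mg-scored contrast plus rising estimates errs in 13% of the same trials, and does worse on a flat 1.3 SD effect (16% against 7%). A trend test also adds little power: 1 to 5 percentage points over 800 mg versus placebo, for a linear response with an 800 mg effect of 0.5 to 1.25 SD. So a trend contrast is not the main remedy. The case for 800 versus 200 mg stands, because it addresses the rise directly.

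On the outcomes, a reader might infer that there is no hierarchy at all, or that multiplicity is severe. The CPT section singles out the two latencies and the SAP lists the ratings after them, so the hierarchy is incomplete rather than absent. The two latencies alone give about 5% familywise error. What stands is that neither latency is ranked above the other, and the ratings receive the same comparisons with no stated lesser status.

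The SAP is written in the past tense and the file is dated 02/23/21. If the analysis is done, new choices carry only post hoc weight. That limits the remedy but does not remove the gap.

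**Conclusion.** The concern holds in a limited form. The placebo comparisons remain valid and informative, but none compares active doses, and their joint significance is equally likely (62%) under a shallow rise and a mild fall. Lack of a single primary pain measure raises the chance of any false positive from about 2.7% to about 8-10%. This is modest; the larger defect is that nothing says how conflicting measures are to be read. The contradiction over subjective effects is direct and needs no calculation.

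The textual findings are firm. The percentages depend on the assumed effects, on one value per session and on sphericity, none of which the documents supply. For example, with contrast-specific error (17 df) the mg contrast is significant in 85% of steep-rise and 38% of flat 1 SD trials, rather than 91% and 44%. This is worth correcting, but it does not undermine the trial.

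**What to change.** 1. Name one of the two latencies as the primary pain measure. Treat the other latency and the two ratings as supportive, and show the ratings alongside immersion time.
2. Keep the three placebo comparisons. On the primary measure, pre-state the 800 versus 200 mg difference with its confidence interval as the direct evidence on dose-dependence, and say that its power is low at N = 18. An ordered contrast with stated scores may be added as a supplement, not as a gatekeeper, noting that it includes placebo and so also responds to a flat effect.
3. Make the two statements in the General Investigational Plan agree on whether subjective effects are primary or secondary.
4. If the data have already been analysed, label the added comparison and the choice of primary measure as post hoc.

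The cost is wording and one extra comparison on data already planned for collection. The drawbacks are that supportive measures can no longer be claimed as primary, and that the active-dose comparison will often be inconclusive.
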